### **1.3.3. Summary of Clinical Safety**

Up to 1 January 2014, an estimated 2409 patients are available for safety analysis of obinutuzumab in clinical trials. These include patients with CLL or NHL, from doses of 50 mg to 2000 mg in monotherapy or in combination with CHOP, FC, bendamustine, or chlorambucil. To date, the largest and most mature dataset available to assess the safety of obinutuzumab as monotherapy comes from studies BO20999 and BO21003; the largest and most meaningful dataset to assess the safety of obinutuzumab in combination therapy with chlorambucil comes from study BO21004. Overall, most of the safety experience is based on NHL patients currently undergoing treatment with 1000 mg obinutuzumab; however these data currently remain blinded and therefore contribute little to the assessment of the safety profile of obinutuzumab. There is only limited post marketing experience.

The following adverse events are considered as important risks associated or potentially associated with obinutuzumab: Infusion related reactions, tumor lysis syndrome, thrombocytopenia including acute thrombocytopenia, neutropenia, late onset and prolonged neutropenia, prolonged B-cell depletion, infections including Progressive multifocal leukoencephalopathy and hepatitis B reactivation, gastro-intestinal perforation, worsening of pre-existing cardiac conditions, impaired immunization response, immunogenicity, and second malignancies. Most of these are briefly discussed.

The most frequently observed adverse drug reactions (ADRs) in patients receiving obinutuzumab were infusion-related reactions (IRR); these occurred predominantly during the first infusion. The incidence and severity of infusion related symptoms decreased substantially with subsequent infusions, with most patients having no IRRs during the second and subsequent administrations of obinutuzumab. Patients with a high tumor burden (ie, high peripheral lymphocyte count in CLL ( $>25 \times 10^9/L$ ) may be at increased risk of severe IRR. The commonly experienced IRRs are characterized by hypotension, fever, chills, flushing, nausea, vomiting, hypertension, and fatigue, among other symptoms. In the majority of patients, IRRs were mild or moderate and could be managed. Hypersensitivity may be difficult to distinguish from infusion-related reactions; anaphylaxis has been reported in patients treated with obinutuzumab.

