##### **1.3.4.1. Risk of IRR**

The most frequently observed IRRs were characterized primarily by hypotension, fever, chills, flushing, nausea, vomiting, hypertension, dyspnea and fatigue. IRRs occurred predominantly during the first infusion, and their incidence and severity decreased rapidly with subsequent infusions. Some patients developed severe IRRs requiring permanent discontinuation of obinutuzumab. Although inconclusive, IRRs appear to be more frequent and/or more severe in patients with large tumor volume (eg, peripheral lymphocytosis, diffuse bone marrow involvement, bulky or high tumor masses). This is most predominantly the case in CLL, but may also be present in other forms of lymphomas. All patients should be premedicated as recommended in the study protocols. Patients who develop IRRs should receive supportive care, and if necessary the infusion should be slowed, interrupted, or split over 2 days.

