##### **5.3.2.2. Premedication**

All subjects should be premedicated with acetaminophen/paracetamol to reduce the risk of obinutuzumab related infusion reactions, as detailed in Table 2 below.

Subjects with a history of cardiac disease should be monitored closely. In addition these subjects should be hydrated with caution in order to prevent a potential fluid overload. Hypotension may occur during obinutuzumab administration. Consider withholding antihypertensive treatments for

12 hours prior to and throughout each obinutuzumab infusion and for the first hour after administration.

**Table 2: Premedication to be Administered Before Obinutuzumab Infusion to Reduce the Risk of Infusion Related Reactions (Mandatory for CLL Subjects Receiving the First Dose)**

Day of Treatment Cycle	Subjects requiring premedication	Premedication	Administration
Cycle 1: Day 1	All subjects	Intravenous corticosteroid 	Completed at least 1 hour prior to obinutuzumab infusion.
		Oral analgesic/anti-pyretic 	At least 30 minutes before obinutuzumab infusion.
		Anti-histaminic drug 	
Cycle 1: Day 2	All subjects	Intravenous corticosteroid 	Completed at least 1 hour prior to obinutuzumab infusion.
		Oral analgesic/anti-pyretic 	At least 30 minutes before obinutuzumab infusion.
		Anti-histaminic drug 	
Cycle 1: Day 8, Day 15	Subjects with a Grade 3 IRR with the previous infusion OR subjects with lymphocyte counts $>25 \times 10^9/L$ prior to next treatment	Intravenous corticosteroid 	Completed at least 1 hour prior to obinutuzumab infusion.
Cycles 2-6: Day 1	All subjects	Oral analgesic/anti-pyretic 	At least 30 minutes before obinutuzumab infusion.
	Subjects with an IRR (Grade 1 or more) with the previous infusion	Anti-histaminic drug 	

1. 20 mg dexamethasone or 80 mg methylprednisolone or equivalent given intravenously. Hydrocortisone should not be used as it has not been effective in reducing rates of IRR.

2. eg, 1000 mg acetaminophen/paracetamol

3. eg, 50 mg diphenhydramine

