1.2.2. Secondary Endpoints

- PFS by IRC in high risk analysis set
- Rate of sustained hemoglobin improvement
- Rate of MRD-negative response
- ORR by IRC
- OS
- Rate of infusion related reactions
- Rate of sustained platelet improvement
- Rate of clinically meaningful improvement in EQ-5D-5L utility score

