1.6. Testing Procedure and Level of Significance

To preserve the study wise type I error rate of 0.05, the primary and secondary endpoints will be tested based on a serial gatekeeping testing procedure at the two-sided significance level of 0.05 according to the hierarchical order as listed in 1.2.2.

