4. ANALYSIS FOR ENDPOINTS

Analysis of endpoints will be conducted on the ITT population, unless otherwise specified. Table 1 summarizes the efficacy endpoints and analysis methods to be performed.

The following two randomization stratification factors will be used for the stratified analysis/test: ECOG performance status (0, 1 versus 2) and Cytogenetics (del 17p, del 11q without del 17p, others). To reflect the randomization process and maintain the integrity of randomization, all stratified tests will be based on randomization stratification factors as recorded in the IWRS.

For subgroup and exploratory analysis, only the analysis that provide meaningful information will be presented.

Table 1: Definitions and Analyses for Endpoints

Endpoint	Definition	Analysis Method
Primary Endpoint		
PFS assessed by IRC	Time from the date of randomization to the date of IRC-assessed disease progression or date of death from any cause, whichever occurred first, regardless of the use of subsequent antineoplastic therapy prior to documented PD or death.	
Primary Treatment effect of ibrutinib plus obinutuzumab compared to chlorambucil plus obinutuzumab was tested with a log-rank test. The hazard ratio and its 95% CI based on a Cox regression model are calculated. PFS distribution is estimated by Kaplan-Meier method: median PFS and landmark estimates with 2-sided 95% CIs are to be provided for each treatment arm.
 
Sensitivity Analyzing PFS assessed by investigator using the same method as PFS assessed by IRC.
 
Subgroup Hazard ratio and its 95% CI based on unstratified Cox regression model for each subgroup.

Secondary Endpoints		
PFS assessed by IRC in high risk analysis set	Defined the same as the primary endpoint.	Analyzed the same as primary endpoint in high risk analysis set
ORR assessed by IRC	The proportion of subjects achieving a best overall response of CR, CRi, nPR, or PR per IRC assessment at or prior to initiation of subsequent antineoplastic therapy.	Chi-square test.
Overall survival (OS)	Time from the date of randomization to the date of death from any cause. All deaths observed at the time of the analysis will be considered as events. For subjects who were not known to have died at the time of the analysis, OS data will be censored at date last known alive.	Analyzed the same as PFS primary analysis.

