Rate of MRD-negative response	Proportion of subjects who achieved MRD-negative response defined as < 1 CLL cell per 10,000 leukocytes as assessed by flow cytometry of a bone marrow aspirate or peripheral blood sample per central laboratory.	Chi-square test for MRD-negative response rate by bone marrow

- Rate of infusion related reactions will be analyzed using a Chi-square method.
- Rate of sustained platelet improvement will be analyzed using a Chi-square method
- Rate of clinically meaningful improvement in EQ-5D-5L utility score will be analyzed using a Chi-square method

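### The infusion-reaction comparison in the controlled testing sequence is a valid but unadjusted chi-square; stratifying it by pre-dose lymphocyte count would cost nothing and could recover some power if the count is predictive

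*SAP*

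**What the plan says.** SAP section 1.2.2 lists "Rate of infusion related reactions" as the sixth of eight secondary endpoints. Section 1.6 has the primary and secondary endpoints "tested based on a serial gatekeeping testing procedure at the two-sided significance level of 0.05", in the listed order. Counting the primary, this is the seventh test. It follows overall survival (OS) and precedes sustained platelet improvement and EQ-5D-5L improvement.

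The analysis is one line after Table 1 of SAP section 4: "Rate of infusion related reactions will be analyzed using a Chi-square method". On stratification, the same section says: "The following two randomization stratification factors will be used for the stratified analysis/test: ECOG performance status (0, 1 versus 2) and Cytogenetics". It adds that every stratified test takes its factors from the randomization system. Lymphocyte count is not one of them.

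The protocol mentions the count in three places:
- Section 1.3.3: patients with a high count (above 25 x 10^9/L) "may be at increased risk of severe IRR".
- Section 1.3.4.1: "Although inconclusive, IRRs appear to be more frequent and/or more severe in patients with large tumor volume (eg, peripheral lymphocytosis", among other signs of large tumor volume.
- Section 5.3.2.2, Table 2: the same threshold is one trigger for steroid premedication on Cycle 1 Days 8 and 15 ("Subjects with a Grade 3 IRR with the previous infusion OR subjects with lymphocyte counts" above it).

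Lymphocytes are part of the hematology panel (Protocol 7.1.2.1), which is taken at Screening (8.1.1) and before dosing on Cycle 1 Day 1 (8.2.1.1).

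**The concern.** A baseline variable that predicts a binary outcome can be used to sharpen the comparison between arms. Here the protocol itself points to a candidate, gives a cut-point and collects the value before treatment, but neither the randomization nor the analysis uses it. If the count does predict IRRs, the plain chi-square leaves variation unexplained that a stratified test would remove, and some power may be lost.

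The stake extends beyond this endpoint. In a serial procedure, a non-significant IRR result also ends formal testing of the platelet and EQ-5D-5L endpoints.

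**Working it through.** **Plan's own figure.** The documents state no power or sample size for the IRR test. The one design figure, 94 PFS events, reproduces with Freedman's formula: (1.55/0.45)^2 x (1.960 + 0.842)^2 = 93.1, rounded up to 94. SAP section 1.4 gives about 212 subjects at 1:1, so n = 106 per arm. (The OS paragraph in Protocol 10.7.2.3 uses 229.)

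**Assumed inputs, because the documents give none.** IRR rate in Arm B 30%, 45% or 60%. Arm A rate (14.1%, 26.7%, 40.9%) chosen so that the plain chi-square has about 80% power. Share of subjects with a high count 30%, 50% or 70%. Odds ratio (OR) of a high count for IRR from 1 to 5.

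**Formula.** Power = Φ[(d − 1.96 s0)/s1], where d is the difference in rates.
- Plain test: s0² = 2p̄(1 − p̄)/n and s1² = [pA(1 − pA) + pB(1 − pB)]/n.
- Stratified test: the same terms computed within each count stratum and averaged with weights equal to the stratum shares.

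**One case in full.** Take pB = 0.45, pA = 0.267, half the subjects with high counts and OR 3.
- Plain: d = 0.183, p̄ = 0.3585, s0 = 0.0659, s1 = 0.0647. (0.183 − 0.1291)/0.0647 = 0.833, so power is 79.8%.
- Stratum rates (low/high count): Arm B 31.7%/58.3%, Arm A 16.4%/37.0%. Then s0 = 0.0639 and s1 = 0.0626. (0.183 − 0.1251)/0.0626 = 0.925, so power is 82.2%.
- Gain: 2.5 points. The same case gives 80.8% at OR 2 (+1.0) and 84.7% at OR 5 (+5.0).

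**Range over all combinations** (gain in points from stratifying):

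| Count OR | Formula | Simulation, 40,000 trials each |
|---|---|---|
| 1 | 0 | −0.6 to +0.4 |
| 2 | +0.6 to +1.1 | +0.2 to +1.7 |
| 3 | +1.2 to +2.7 | +0.9 to +3.5 |
| 5 | +2.2 to +5.5 | +1.8 to +6.2 |

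**A second scenario with lower starting power.** 55% high count, 40% IRR in low-count Arm B subjects, Arm A halving the odds, 100,000 simulated trials per row:

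| Count OR | Chi-square | Stratified | Gain |
|---|---|---|---|
| 1 | 65.0% | 64.7% | −0.3 |
| 2 | 66.6% | 68.0% | +1.4 |
| 3 | 63.2% | 67.3% | +4.1 |
| 5 | 56.3% | 63.8% | +7.5 |

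If Arm A doubles the odds instead, the gains at OR 2, 3 and 5 are 1.7, 2.1 and 5.4 points. Taking both scenarios together gives about 1 to 2, 1 to 4 and 2 to 8 points.

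**Validity.** Simulated type I error was 4.5% to 4.7% for the chi-square and 4.9% to 5.0% for the stratified test.

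**Chance imbalance.** With 55% high counts, the 95% range for the between-arm difference in that share is ±1.96 x √(2 x 0.55 x 0.45/106) = ±13.4 points. At OR 3 the high-count rate is 66.7% against 40%, so an imbalance at that limit moves the crude difference by 0.134 x 26.7 = 3.6 points. At OR 5 (76.9% against 40%) it moves it by 4.9 points.

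**Effect of position.** Counting OS alone (about 69% stated power) and treating the tests as independent, a 2-point gain becomes 0.69 x 2 = 1.4 points.

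**The case against.** The strongest reply is that nothing is wrong. An unadjusted chi-square is valid in a randomized trial, and it is the test SAP section 4 names for its other binary secondary endpoints. A reader might infer that chance imbalance in lymphocyte count biases the comparison. It does not: the test's error rate already allows for random imbalance, and the simulated type I error bears this out. This part stands; only efficiency is at issue.

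A reader might also infer that the protocol establishes the count as a risk factor for IRRs, so that power is certainly lost. The documents do not support that. Section 1.3.3 is hedged and concerns severe IRRs, while the SAP endpoint has no stated severity limit. Section 1.3.4.1 calls the link inconclusive. No association size is given.

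Premedication could weaken the link further. Table 2 gives all subjects the same premedication on Cycle 1 Days 1 and 2, and adds a count-based steroid trigger on Days 8 and 15. The later trigger matters less, because the protocol says IRRs occur predominantly with the first infusion. The calculations model neither.

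Two further points stand. The test comes late in the sequence, so this choice is not the main limit on a formal IRR claim. And the SAP does not define the IRR rate by grade or cycle, while Protocol 10.8.4 splits it by both. SAP section 4 defaults to the ITT population, while section 5 uses the safety population for safety data. The value of adjustment cannot be tied to the endpoint until that is settled.

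What the objection does not supply is a reason to leave the information unused: when the count is not predictive, stratifying changed simulated power by no more than 0.6 points either way.

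**Conclusion.** A free improvement. The planned test is valid but unadjusted, and a candidate predictor flagged by the protocol is already measured before the first dose. If the count is predictive, some power may be lost: nil at OR 1, about 1 to 2 points at OR 2, about 1 to 4 at OR 3 and about 2 to 8 at OR 5. These figures rest wholly on assumed IRR rates, count distribution and treatment effect, with 106 subjects per arm. The upper figures need a strong association, for which the documents offer no evidence. The documents do not support a firmer statement that power is lost, or that the analysis is biased. The practical effect is further limited because all earlier tests must succeed first, but a failure here would also stop the platelet and EQ-5D-5L tests.

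**What to change.** Before database lock, make three changes to SAP section 4:

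1. Make the test for this endpoint a Cochran-Mantel-Haenszel test stratified by the last lymphocyte count before the first dose of any study drug (above 25 versus 25 x 10^9/L or below), with the common risk difference and its 95% CI. The reference must be the first dose of any study drug because Protocol 8.2.1.1 gives the oral drug before obinutuzumab; later counts can be altered by treatment.
2. Keep the plain chi-square as a supportive analysis.
3. Amend the sentence that ties all stratified tests to the factors recorded in the randomization system, so that it allows this exception. Without this, the new test would contradict the SAP.

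The same edit is the natural place to state the grade, cycle window and population for the IRR rate.

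The cost is SAP wording and one changed procedure. No new data are needed.

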5. SAFETY ASSESSMENTS

Safety data will be summarized for the safety population. Table 2 summarizes the safety analyses to be performed.

Adverse events will be coded in accordance with the MedDRA. Severity of AEs will be graded by the investigator according to the NCI-CTCAE v4.03 for non-hematological AEs and IWCLL 2008 guidelines for hematologic toxicity.

Treatment-emergent period is defined as the period from the date of the first dose of study treatment up to 30 days after the date of the last dose of study treatment or the day before initiation of subsequent antineoplastic therapy (including the cross-over ibrutinib monotherapy for arm B subjects), whichever comes first.

The treatment-emergent adverse events (TEAE) are those events that occur or worsen during the treatment-emergent period or that are related to the study treatment. Unless otherwise specified, only TEAEs will be included in the adverse event summaries.

All laboratory values will be converted to and reported as international standard (SI) units. In general, only data from the central laboratory will be summarized and analyzed. Hematologic parameters including platelet counts, hemoglobin, and neutrophils will be assessed by the grading scale for hematologic toxicity in CLL studies in the IWCLL 2008 guidelines. All other gradable laboratory parameters will be graded using the NCI CTCAE v4.03. Unless otherwise specified, only baseline and post-baseline values collected during the treatment-emergent period will be included in the safety analysis.

Table 2: Summary of Safety Assessments

Assessment Type	Definition	Analysis Methods
AE	TEAEs, SAEs, Grade 3 or worse TEAEs, related TEAEs, TEAEs leading to treatment discontinuation, TEAEs leading to dose reduction, TEAEs leading to death, protocol-defined events of special interest and other safety observations. TEAEs within the first 9 months of study treatment and TEAEs in the crossover period	Descriptive summary statistics and/or listings
Lab	Worst post-baseline toxicity grade for selected CTCAE gradable hematology and chemistry. Abnormalities in creatinine clearance, uric acid, and liver function	Descriptive summary statistics and/or listings
Vital Signs and other Observations Related to Safety	Blood pressure, heart rate, new or worsened eye-related symptoms	Descriptive summary statistics and/or listings

TEAE= treatment-emergent adverse event; SAE= serious adverse event; CTCAE= Common Terminology Criteria for Adverse Events.

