**10.8.1. Adverse Events (AEs)**

Adverse events (AEs) will be graded by the Investigator according to the NCI CTCAE v4.03 for non-hematological AEs. Hematologic toxicity will be assessed by the IWCLL 2008 criteria for grading hematologic toxicity in CLL studies. Verbatim descriptions of AEs will be coded using the current version of the Medical Dictionary for Regulatory Activities (MedDRA). Adverse events that started from the date of the first dose of the first study drug up to 30 days after the date of the last dose of the last study drug, or the first date starting new anticancer therapy, whichever is earliest, are considered treatment-emergent except treatment related AEs. Any treatment related AE will be considered treatment-emergent regardless of the start date of the event. Any event that is present at baseline but worsens in severity or is subsequently considered treatment-related by the investigator will also be considered as treatment-emergent. All-treatment emergent AEs will be summarized by treatment arm. The incidence rates of treatment-emergent AEs will be summarized by System Organ Class (SOC), preferred term, toxicity grade, and relationship to study drug. In addition, SAEs, Grade 3 or above AEs, AEs leading to study treatment discontinuation, delay, reduction, or interruption, AEs leading to death, and events of special interest will be summarized. Multiple occurrence of the same event in a given subject will be counted once at the maximum severity and strongest relationship to study drug.

AEs leading to death and non-fatal SAEs will be listed by subject and tabulated by preferred term.

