1. INTRODUCTION

This statistical analysis plan (SAP) lays out key elements including definitions and statistical methods for analysis of data in evaluation of efficacy and safety for the PCYC-1130-CA study. Analyses of pharmacokinetics (PK) data and exploratory analyses for clonal evolution, disease-related mechanisms of resistance and the secreted protein analysis for obinutuzumab-related infusion reactions will be addressed in separate documents.

Throughout this SAP, “study treatment” and “study drug” are used interchangeably.

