2. GENERAL ANALYSIS CONSIDERATION

2.1. Analysis Sets

Intent-To-Treat (ITT) population: defined as all subjects who were randomized. Subjects will be grouped according to the treatment assigned at randomization. This population will be the primary population for the analyses of efficacy endpoints, disposition, demographics and baseline characteristics, baseline disease characteristics, subsequent anticancer therapy and patient-reported outcome data.

Safety population: defined as all subjects who received at least 1 dose of any one of the three study drugs (ibrutinib, chlorambucil, or obinutuzumab). Safety data will be analyzed as treated. The Safety Population will be used to summarize the safety (including dosing and concomitant medications) data.

High risk analysis set: defined as randomized subjects with del17p or TP53 mutation or del 11q at baseline per central lab results.

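### The SAP's treatment-emergent definition has an untimed relatedness limb not restricted to randomized treatment, so read literally it can place crossover-ibrutinib events in Arm B's main adverse event tables

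*SAP*

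**What the plan says.** SAP Section 5 sets up the adverse event tables in four steps.

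- The treatment-emergent period starts at the first dose of study treatment. It ends 30 days after the last dose or "the day before initiation of subsequent antineoplastic therapy (including the cross-over ibrutinib monotherapy for arm B subjects), whichever comes first".
- Treatment-emergent events are "those events that occur or worsen during the treatment-emergent period or that are related to the study treatment".
- The tables are restricted to such events by default: "Unless otherwise specified, only TEAEs will be included in the adverse event summaries".
- Table 2 of the SAP lists, among the planned summaries, "TEAEs within the first 9 months of study treatment and TEAEs in the crossover period".

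Protocol Section 10.8.1 has the same untimed rule in stronger words: "Any treatment related AE will be considered treatment-emergent regardless of the start date of the event". It also says that these events are tabulated by treatment arm.

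On terminology, SAP Section 1 says that study treatment and study drug "are used interchangeably". SAP Section 2.1 names ibrutinib, chlorambucil and obinutuzumab as the three study drugs, with no limit by arm or study phase.

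**The concern.** Arm B subjects may take ibrutinib after IRC-confirmed progression. The SAP closes the treatment-emergent period before that ibrutinib starts, but the relatedness limb sits outside the period. If crossover ibrutinib counts as study treatment, an event attributed to it meets the definition and belongs to an Arm B subject. Nothing in the SAP then removes it from the by-arm tables.

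Any leakage runs one way. It adds the experimental drug's toxicity to the control arm and narrows the contrast on the risks the protocol lists for ibrutinib, such as bleeding, atrial fibrillation and hypertension (Protocol Sections 1.2.4.1, 1.2.4.2 and 1.2.4.12). Major hemorrhage is exposed as well: Protocol Section 11.4.6.1 defines it through treatment-emergent events, and SAP Table 2 tabulates the protocol's events of special interest.

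**Working it through.** **1. Does the relatedness limb have a time limit?** No. In the SAP it is joined by 'or' to the limb that uses the period, and it carries no window of its own. Protocol Section 10.8.1 says outright that the start date does not matter.

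**2. Is crossover ibrutinib study treatment?** The documents point both ways.

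| Points to yes | Points to no |
|---|---|
| SAP 1 and 2.1: the two terms are equated and ibrutinib is a study drug without restriction | SAP 5: crossover ibrutinib is classed as subsequent antineoplastic therapy |
| Protocol Appendix I: crossover ibrutinib is listed under study drug administration, with adverse events collected | Protocol 10.7.3.2: next-line ibrutinib counts as subsequent treatment for time to next treatment |
| Protocol 8.4.1, criterion 5: next-line ibrutinib is called study drug | Protocol 7.2.6 and 9.2: study treatment stops at progression |
| Protocol synopsis: next-line ibrutinib appears in the study treatment row | Protocol synopsis, study design row: randomized treatment and crossover therapy are named separately |

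**3. What does the crossover item in SAP Table 2 imply?** The only period the SAP defines ends before crossover. An event starting after crossover can then be treatment-emergent only through the relatedness limb. So either that limb covers crossover ibrutinib, or the table relies on a crossover period that is never defined. Listing such events separately does not by itself take them out of the main tables.

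**4. Is the cut-off consistent within the section?** No. SAP Section 5 limits laboratory values to the treatment-emergent period unless otherwise specified. Adverse events and laboratory data in Arm B could then follow different cut-offs.

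**5. How many subjects could cross over?** The inputs are from SAP Section 1.4: control median PFS 27 months, hazard ratio 0.55, 94 events, 18 subjects per month, 212 subjects randomized 1:1, about 36 months.

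The plan's event count reproduces with Freedman's formula at 80% power and two-sided 5%:

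(1.960 + 0.842)² × [(1 + 0.55)/(1 − 0.55)]² ≈ 7.85 × 11.86 ≈ 93.1, rounded up to 94.

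For timing, assume exponential PFS, uniform accrual over R = 212/18 = 11.8 months and no dropout. With λ = ln 2 / median, the expected proportion with an event by month T is

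1 − [exp(−λ(T − R)) − exp(−λT)] / (λR).

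| T (months) | Arm B, of 106 | Arm A, of 106 | Total |
|---|---|---|---|
| 36 | 56.9 | 36.6 | 93.5 |
| 48 | 69.9 | 47.4 | 117.3 |

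The 36-month total agrees with the planned 94. About 57 of 106 Arm B subjects (54%) have a PFS event by then, and about 70 (66%) by 48 months, roughly when follow-up ends (SAP Section 1.5.3). Both are ceilings on crossover: PFS events include deaths, and crossover requires IRC confirmation, the criteria in Protocol Section 8.4.1 and approval.

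**The case against.** The strongest reply is that the SAP already separates crossover from randomized treatment. The sentence just before the definition contrasts study treatment with subsequent therapy and puts crossover ibrutinib in the second group. Read in that light, relatedness refers to the treatment whose doses set the period. The separate crossover summary would be odd if those events were meant for the main tables. This probably describes the intention. It does not settle the wording, because the classification as subsequent therapy limits only the first limb and the documents elsewhere call crossover ibrutinib study drug.

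Three further points carry weight.

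- The untimed limb has a proper purpose. Protocol Section 1.3.4.4 reports PML about 2 years after obinutuzumab was stopped. Late events related to chlorambucil or obinutuzumab belong in Arm B, so the limb should be narrowed and not deleted.
- The summary of the first 9 months is less exposed, but it is not immune. Under the plan's exponential assumption, 1 − 2^(−9/27) = 21% of Arm B has a PFS event within 9 months of randomization. It also does not replace the full-period tables.
- Reliance on an unblinded causality judgement comes with an open-label design and is not a separate defect.

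A reader might go further and infer that the plan sets out to pool crossover toxicity with Arm B, or might put a percentage-point inflation on Arm B's event rates. The documents support neither. The crossover provisions point away from pooling. No crossover rate or ibrutinib-related event rate is given for this setting. Multiplying assumed rates would also overstate the effect: Protocol Section 10.8.1 counts a repeated event once per subject, so a subject who already had that event on randomized treatment adds nothing to its incidence.

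**Conclusion.** The definition needs correcting. Followed literally, it allows events related to crossover ibrutinib into Arm B's main descriptive tables, against the SAP's own cut at crossover. Two programmers could derive different Arm B tables from the same text.

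Only events judged related to ibrutinib would enter, and the effect would be to make Arm A look relatively safer. The size cannot be stated. The one bound available is about 57 of 106 Arm B subjects at the primary analysis. It rests on exponential PFS, the design medians, uniform accrual and no dropout, and true crossover will be lower.

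No hypothesis test or type I error is affected. Adverse event summaries are descriptive, and the tested infusion-reaction endpoint is not touched because crossover ibrutinib is an oral monotherapy.

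**What to change.** In SAP Section 5:

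- Change the relatedness limb to read *or that are related to the randomized study treatment*. This keeps late chlorambucil- or obinutuzumab-related events in Arm B.
- Define a crossover treatment-emergent period that starts at the first crossover ibrutinib dose, and state how it ends.
- State that events related to crossover ibrutinib appear only in the crossover summary.

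Align Protocol Section 10.8.1 with this wording.

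The cost is a few sentences and one programming flag based on the first crossover dose date. No new assessments are needed. The programmer should confirm that the causality field can tell crossover ibrutinib from the randomized drugs for events after that date. If it cannot, the SAP should state a default attribution.
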